## **12.2 Data Capture and Analysis**

All data will be recorded on 2-part NCR paper Case Report Forms (CRFs). The surgeon will complete and sign forms at the time of completion. Original CRFs will be collected by Stryker for data entry. Copies will remain at the investigator site. Archiving will be undertaken in accordance with ICH/GCP guidelines (Appendix 6).

Any unclear or ambiguous data will be queried and all cleaned data will be entered into a database for tracing purposes.

The primary outcome data gathered from Group A will be assessed using a repeated-measures analysis (Hopkins, 2009) to determine the mean and standard error of measurement between successive pairs of trials. Multiple surgeons gathering repeated measures on individual patients will be pooled to take into account varying knee anatomies and intra-observer variation.

The data from Group B and the Extension Study will be summarised and descriptive statistics will be utilised for analysis of the primary and secondary outcomes. The mean, median, standard deviation, minimum and maximum will be presented for quantitative variables. Statistical tests will be employed as deemed appropriate by a biostatistician. A significance level of 0.05 will be used for comparative tests.

Adverse events will be tabulated separately and reviewed for any commonalities.

Revision surgery data from the Extension Study will be compared to the revision rates reported in the National Joint Registry Report at 12 months, 2 years and 5 years. A cost benefit analysis will be undertaken with the use of data from the Australian Government Hospital Casemix Protocol Annual Report.

A formal interim analysis will take place following completion of each Group A and Group B sub-studies. Additionally, formal interim analyses will take place following all

participants' completion of the 12 month visit, again following completion of all participants' 2 year visit and final analysis will take place following completion of all participants' 5 year follow-up visits.

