### **3.0 OBJECTIVES**

The primary endpoints of this study are:

1. Repeatability of cutting guide position on the distal femur and proximal tibia assessed by repeated measures using computer navigation system for total knee replacement, assessed intra-operatively (Group A).
2. Radiographic implant location, consisting of multi-parameter assessment of the relative position and orientation of the femoral and tibial components and overall limb alignment, assessed by the Perth CT protocol 3 months after surgery (Group B).

The secondary endpoint of this study is:

3. Knee function, quality of life and pain assessed 6 months after surgery (Group B).

The study objectives are:

1. Repeatability of the cutting guide position will be no worse than that obtained for manual instruments used for total knee replacement (Group A).

2. Participants will have higher knee function scores and increased quality of life as compared to pre-operative state and equal or better as compared to other surgical techniques using historical controls (Group B)

The objectives of the Extension Study are:

1. The primary objective is to determine the clinical and radiographic outcomes at 12 months, 2 years and 5 years post surgery, in patients receiving a Triathlon Custom Fit Knee featuring Stryker ShapeMatch.
2. The secondary objective is to determine the revision rate (yearly cumulative percent revision), device-related adverse events and reoperation rates.

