## RESEARCH OBJECTIVES

The use of patient-specific cutting guides for total knee joint replacement is being developed and introduced to clinical practice by a number of orthopaedic device companies. Each system differs in the way in which the cutting guides are designed, the material which they are made from, the alignment philosophy and the radiological information on which they are based (e.g. X-ray, CT, MRI).

The overall goal of this study is to assess the impact of a new surgical technique developed by Stryker on the functional outcome of participants undergoing primary total knee joint replacement.

The repeatability in placing the cutting guides relies on the reference points used in the design of the block, and the ability of the surgeon to position it on the diseased joint surfaces of the knee without the availability of traditional alignment jigs (femoral intra-medullary rod, tibial extra- or intra-medullary alignment guide). Hence, the first objective of this study is to quantify the reproducibility of this new technique by assessing cutting guide position using a repeated-measures methodology. The results will be described as a standard error of measurement.

Early reports indicate that improved post-operative functional outcomes may result from the use of this new technology when used in combination with particular designs of total knee joint prosthetic components (Howell et al, 2008; Spencer et al, 2009). The second objective is to assess and quantify such changes in the short-term (6

months) post-operative period. Potential benefits may be seen in the general quality of life experienced by participants, reduced pain levels, and specific improvements in activities of daily living affected by knee function. Other parameters related to the procedure, such as operating time, blood loss and length of stay in hospital will also be assessed to determine if perceived benefits with the use of this new surgical technique can be realised in routine clinical practice. Comparison of the study findings will be made to published literature on the clinical outcomes of total knee replacement (e.g. Kolisek et al, 2007; Matziolis et al, 2007; Harwin et al, 2008).

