**7.0 STUDY DESIGN**

**Group A:** This is a repeatability study of ShapeMatch® patient-specific cutting guides designed for participants undergoing total knee arthroplasty with the Triathlon® Total

Knee System (Stryker Orthopaedics, Mahwah NJ, USA) and Stryker eNact Knee Navigation System (Stryker Navigation, Kalamazoo MI, USA). Participants will undergo pre-operative assessment using MRI of the affected limb according to the scan protocol (see Appendix 2 for example). At the time of surgery, a repeated-measures methodology will be implemented in which the position of the femoral and tibial cutting guides will be measured using the Navigation system. The same surgeon will position each cutting guide a total of 3 times for each patient. Multiple participants will be assessed by each surgeon. No bone resections will take place using the patient-specific cutting guides. After the study-specific measurements have been taken, the total knee procedure will resume using the Navigation system and associated instruments being used to prepare the distal femur and tibia prior to implantation of the Triathlon® total knee components. No post-operative evaluations will be undertaken as part of this sub-study. However, participants will have routine visits, as per the investigators' standard-of-care for such participants.

Approximately 30 participants (5 per investigator) up to a maximum of 60 participants will contribute to this sub-study.

**Group B:** This is a consecutive sample survey of participants undergoing total knee arthroplasty with the Triathlon® Total Knee System (Stryker Orthopaedics, Mahwah, NJ USA) utilizing ShapeMatch® patient-specific cutting guides to prepare the bony resections on the distal femur and proximal tibia. Health status and functional outcome measures will be recorded to quantify functional status of subjects before surgery and at each follow-up interval.

Participants suitable for primary total knee arthroplasty and indicated for computer-assisted surgery will be booked for surgery. Recruitment will be subject to gaining suitable informed consent from the patient.

Participants will undergo pre-operative assessment using MRI of the affected limb according to the scan protocol (Appendix 2).

Appropriate total knee replacement components from the Stryker Triathlon® Total Knee System will be used.

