## **9.0 SURGICAL PROCEDURES**

### **Group A:**

Each patient will be prepared to undergo a primary total knee replacement using the Triathlon Primary Total Knee System and Stryker eNact Knee Navigation System. A standard skin incision and joint exposure will be performed according to the surgeon's

preference. Navigation trackers will be secured to the femur and tibia and registration of the limb will be undertaken according to the surgical technique.

The appropriate Stryker ShapeMatch® Cutting Guide will be positioned onto the distal femur. A Navigation tracker with Resection Plane Probe attached will be placed into the cutting slot of the cutting guide. The location (position and orientation) of the probe is displayed on the computer screen of the Navigation system. The screen will be diverted from the surgeon's view and a recording will be made of the position once the surgeon has indicated that the cutting guide is positioned appropriately. The cutting guide will then be removed from the femur, and the process repeated until a total of three measurements have been recorded. The same procedure will be performed on the proximal tibia using the appropriate Stryker ShapeMatch® Cutting Guide. This entire process should take no longer than 5 minutes.

Once these measurements have been performed, the surgeon will resume the surgical technique for implantation of the Stryker Triathlon Primary Total Knee System using Stryker eNact Knee Navigation System, as per their own instrument and implant preferences.

Appropriate post-operative care will be provided according to the preference of the treating physician. No further evaluations will be required by study participants.

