## **12.0 STATISTICAL METHODS**

### **12.1 Sample Size Justification**

#### **Group A**

No published data currently exists on the reliability and repeatability of the ability of surgeons to position the patient-specific cutting guides on the femoral and tibial bone surfaces. This is an observational case series with no sample size calculation. The study uses a sample size of convenience, based on the number of study sites and anticipated recruitment rate at each site.

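### Group A repeatability: the SEM is taken between successive pairs of placements, with no rule for combining the two pairs, although one analysis of all three would be more precise at no data cost

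*Combined protocol and SAP*

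**What the plan says.** Group A has three placements per guide per knee. Section 7.0 states: "The same surgeon will position each cutting guide a total of 3 times for each patient". Section 9.0 has the guide taken off between recordings and "the process repeated until a total of three measurements have been recorded", with the same done on the tibia.

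Section 12.2 sets a repeated-measures analysis of these data "to determine the mean and standard error of measurement between successive pairs of trials". The next sentence covers pooling: "Multiple surgeons gathering repeated measures on individual patients will be pooled to take into account varying knee anatomies and intra-observer variation". That is pooling over surgeons and patients. Nothing is said about combining the comparison of placements 1 and 2 with that of placements 2 and 3, and no SEM formula is given.

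The research objectives in Section 3.0 say: "The results will be described as a standard error of measurement". Objective 1 in the same section is that guide repeatability be no worse than with manual instruments; no margin or reference value is stated. The planned size is "Approximately 30 participants (5 per investigator) up to a maximum of 60 participants", and Section 12.1 adds: "This is an observational case series with no sample size calculation".

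**The concern.** Three placements yield two successive comparisons, so the plan as worded produces two SEMs for every bone and parameter. The text promises a single SEM without saying how to get there. Two things follow.

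- **Precision.** Each pairwise SEM ignores one of the three placements. With about 30 knees and no sample size calculation, precision is limited, and the third placement has already been collected in theatre.
- **Meaning.** If the SEM is built from the SD of paired differences, any shift common to all knees is subtracted out. The SEM then describes random placement error only, and the systematic part sits in the separately reported mean. The plan does not say which of these objective 1 relies on.

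At stake are the width of the interval around a primary result and a clear definition of the figure that will be compared with manual instruments.

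**Working it through.** The documents give no SEM, precision target or calculated sample size for Group A, so there is no stated figure to reproduce.

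**Inputs from the documents.** Three placements per knee by one surgeon (Sections 7.0 and 9.0); n = 30 knees (6 investigators × 5), maximum 60 (Sections 4.0 and 7.0).

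**Assumptions, not in the documents.** Independent normal placement errors with common variance σ²; pairwise SEM = SD of differences / √2; no allowance for error variance differing between surgeons.

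**Degrees of freedom (df) of the SEM variance estimate**

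1. One pair: n − 1 = 29.
2. Two pair variances averaged: the differences (2 − 1) and (3 − 2) share placement 2 and correlate −0.5, so their sample variances correlate 0.25. The average has (1 + 0.25)/2 = 0.625 times the variance of one pair's estimate, giving (n − 1)/0.625 = 1.6(n − 1) = 46.4.
3. All three placements with an order term: 2(n − 1) = 58.
4. All three placements without an order term: 2n = 60.

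The loss relative to line 3 is 1 − 29/58 = 50% for one pair and 1 − 46.4/58 = 20% for the average. A simulation of 40,000 replicates at n = 30 gave effective df of 29.0, 46.5, 57.8 and 60.0 for lines 1 to 4.

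**95% CI factors for the SEM**, √(df/χ²) at the 97.5% and 2.5% points of the chi-square distribution:

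| Analysis | df, n = 30 | Factors | df, n = 60 | Factors |
|---|---|---|---|---|
| One pair | 29 | 0.80–1.34 | 59 | 0.85–1.22 |
| Two pairs averaged | 46.4 | 0.83–1.25 | 94.4 | 0.88–1.17 |
| All three, order term | 58 | 0.85–1.22 | 118 | 0.89–1.15 |
| All three, no order term | 60 | 0.85–1.22 | 120 | 0.89–1.14 |

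At 30 knees the interval width, as a multiple of the estimate, is 1.344 − 0.796 = 0.548 for one pair, 1.255 − 0.832 = 0.423 for the average and 1.222 − 0.847 = 0.375 for all three with an order term. A single pair needs about 60 knees, the Group A maximum, to match what all three placements give with 30.

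**Common drift.** Let every knee shift by δ per placement, so the three expected positions are 0, δ and 2δ, whose sample variance is δ². With σ = 1 (the drift sizes are illustrative):

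| Version of the SEM | Formula | δ = 0.5 | δ = 1.0 |
|---|---|---|---|
| Pairwise, SD of differences / √2 | √σ² | 1.00 | 1.00 |
| All three, order term | √σ² | 1.00 | 1.00 |
| All three, no order term | √(σ² + δ²) | 1.12 | 1.41 |
| Pairwise, uncentred root mean square | √(σ² + δ²/2) | 1.06 | 1.22 |

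Using all three placements therefore does not by itself bring drift into the SEM; leaving out the order term does. Drift that varies from knee to knee is only partly excluded: with a knee-specific drift SD of 0.5, the simulated pairwise SEM was 1.06 against 1.12 from either three-placement version.

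**The case against.** The strongest reply is that the plan is incomplete here rather than wrong. It speaks of pairs in the plural within a repeated-measures analysis, and of one SEM as the result, so averaging the two pairs is a natural reading. The loss is then 20%, and at 60 knees the factors are 0.88–1.17 against 0.89–1.15, which is a small gain. This stands: 50% is the worst case, not the expected one.

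A reader might also infer that the plan hides drift and so flatters the guides. The documents do not support that. The same sentence calls for the mean between successive pairs, where a common drift would appear, and the mean shift from placement 1 to 3 is the sum of the two reported shifts. The SEM formula is not given, the cited statistics source was not available for this review, and no drift size is stated. Section 9.0 also turns the screen away from the surgeon, which limits learning from feedback. Reporting systematic shift apart from random error is a legitimate choice.

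Separate pairwise SEMs have a use as well: they show whether error changes with familiarity, which one pooled SD would conceal. That is a reason to retain them as descriptive output.

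Finally, objective 1 has no margin or reference value, so a narrower interval cannot by itself settle it. That is a larger gap, and this change does not close it. The gain in precision and the need for one defined headline figure remain.

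**Conclusion.** The point holds as a free improvement. The planned pairwise SEM is not invalid, but it uses the three placements inefficiently and leaves the headline figure undefined. The cost at 30 knees is 50% of the degrees of freedom if a single pair is relied on and 20% if the pair variances are averaged; the plan does not say which. Against one pair, the joint analysis narrows the interval by about 31% (1 − 0.375/0.548); against the average, by about 11% (1 − 0.375/0.423).

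On drift the conclusion is narrower. If the SEM is the SD of differences over √2, common drift is absent from the SEM and present in the mean. It would be tempting to conclude that a drift-inclusive SD must decide objective 1. The documents do not support that, because they do not say whether the manual-instrument figure includes drift.

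The degrees of freedom rest on independent normal errors with equal variance across knees and surgeons.

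**What to change.** In Section 12.2, for each bone and each position or orientation parameter:

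- Make the headline SEM the within-knee SD from one repeated-measures model of all three placements, with knee as a random effect and placement order as a fixed effect, and give its 95% CI.
- Report the estimated order effect beside it, and the within-knee SD without the order term as a sensitivity result.
- Keep the SEMs for placements 1–2 and 2–3 as descriptive output, and state the formula used.
- For objective 1, state that the version used will be the one that matches how the manual-instrument figure was derived.

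The cost is a change of wording and a standard model on data already being collected, with no added theatre time or burden on participants. Section 18.0 requires written ethics committee approval for any protocol change, so it needs an amendment.

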All implanted prosthetic components (Stryker Triathlon Primary Total Knee System) used in this study are TGA approved for sale and use in Australia. This study was originally to be undertaken via the Clinical Trial Notification (CTN) Scheme of the Therapeutic Goods Administration (Therapeutic Goods Act, 1989); however the ShapeMatch® Cutting Guides are now also listed on the Australian Register of Therapeutic Goods (ARTG) for sale and use in Australia.

This study will adhere to all relevant requirement and guidelines in relation to the conduct of clinical trials, including the Declaration of Helsinki (Appendix 5) and ICH Good Clinical Practice Guidelines, as implemented in Australia (Appendix 6).

An Extension Study will be undertaken to follow Group B patients who consent to continued follow-up. These patients will be followed out to 5 years post-surgery with follow-up visits at 12 months, 2 years and 5 years in order to collect longer term data on radiographic and patient outcomes.

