#### **4.0 NUMBER OF PARTICIPANTS**

Group A: Six investigators will recruit a minimum of 5 cases per investigator and a maximum of 60 cases in total.

Group B: Four hospitals and five investigators will recruit a total of 100 cases.

Extension Study: Participants from Group B will be invited; a maximum of 100 cases will be included.

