#### **5.0 LENGTH OF STUDY AND PATIENT PARTICIPATION**

The enrolment period for Group A is expected to be 3 months or until the required sample size is reached. For Group B, individual study participants will be seen for at least 6 months after surgery. The enrolment period is expected to be 6 months. Therefore it is anticipated that the entire study will take approximately 1.5 years to complete.

At the completion of the 6 month follow-up visit patients will receive an invite to continue participation in the study via enrollment into the Extension Study. Patients

will be required to give informed consent and will need to meet the Extension study inclusion and exclusion criteria (see sections 6.3 and 6.4).

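### The Extension commits only to descriptive summaries of patients who re-consent, so its 12-month to 5-year score means are biased for all recipients if continuing depends on the 6-month score

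*Combined protocol and SAP*

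**What the plan says.** - **Target.** Section 3.0 gives the Extension's primary objective as to "determine the clinical and radiographic outcomes at 12 months, 2 years and 5 years post surgery, in patients receiving a Triathlon Custom Fit Knee". The population named is recipients, not recipients willing to return.
- **Who is followed.** The Summary (1.0) says the Extension will "follow Group B patients who consent to continued follow-up". Section 5.0 adds that patients "will be required to give informed consent and will need to meet the Extension study inclusion and exclusion criteria", and section 10.0 describes the second consent. Section 4.0 says "Participants from Group B will be invited; a maximum of 100 cases will be included". It gives no minimum and no expected uptake.
- **Analysis.** Section 12.2 states that "data from Group B and the Extension Study will be summarised and descriptive statistics will be utilised for analysis", listing mean, median, standard deviation, minimum and maximum. It adds "Statistical tests will be employed as deemed appropriate by a biostatistician". No Extension analysis set, longitudinal model, missing-data method or comparison of continuers with decliners is defined.
- **Data already scheduled.** The Part B evaluation table schedules KOOS, SF-12 and VAS pain before surgery and at 6 weeks, 3 months and 6 months, and the Knee Society score before surgery and at 3 and 6 months. All four recur in the Extension table. The Forgotten Joint Score and the long-leg weight-bearing X-ray appear only there.
- **Outcome-related exits.** Section 6.4 bars revised patients from entering. Section 17.2 lists re-operation of the knee among the reasons for not continuing.

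**The concern.** A mean at 12 months, 2 years or 5 years taken over attenders estimates the mean for all recipients only if continuing is unrelated to outcome. The invitation comes after the 6-month visit, when patients know how the knee has turned out, so a link is plausible. If patients with better 6-month scores continue more often, and the 6-month score predicts later scores, the attenders' mean is too high for the stated population. The protocol schedules the information needed to correct much of this, because decliners have scores up to 6 months, but it plans no use for those scores after that point.

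At stake is how the long-term results read. If a 6-month mean from all of Group B is set beside later means from continuers, a change in who is measured would look like improvement.

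**Working it through.** **Inputs from the documents.** SD 35 and a 15-point clinically significant difference on the Knee Society score (section 12.1). The plan's own figure reproduces: 2 × (1.96 + 0.84)² × 35² / 15² = 85.5, which rounds up to 86, and the exact two-sided t-test gives 86.44, which rounds up to the stated 87. Going from 87 to 100 allows for 13% drop-out. It is not said to cover declining the Extension.

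**Inputs assumed.** The documents give no participation rate p, no strength of selection and no correlation r between the 6-month and later scores. I take r = 0.5 to 0.7 and vary the other two.

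**Formula.** Let z be the standardised 6-month score and let logit P(continue | z) = a + ln(OR) × z, with a chosen so that a proportion p continues. If continuing depends on z alone, then

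bias of the attenders' later mean = r × 35 × E[z | continue].

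| p | OR per SD | E[z given continue] | Excess in 6-month mean (35 × E[z]) | Bias in later mean, r = 0.5 to 0.7 | Share of 15 points |
|---|---|---|---|---|---|
| 90% | 1.5 | 0.040 | 1.4 | 0.7 to 1.0 | 5 to 7% |
| 90% | 2 | 0.066 | 2.3 | 1.2 to 1.6 | 8 to 11% |
| 70% | 2 | 0.190 | 6.65 | 3.3 to 4.7 | 22 to 31% |
| 60% | 3 | 0.354 | 12.4 | 6.2 to 8.7 | 41 to 58% |

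The last row is extreme. It implies a 6-month gap between continuers and decliners of 12.4 / 0.40 = 31 points.

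**Check by another route.** With D the 6-month gap between continuers and decliners, bias = (1 − p) × r × D. For p = 0.60 to 0.90, D = 10 to 20 and r = 0.5 to 0.8, this runs from 0.10 × 0.5 × 10 = 0.5 to 0.40 × 0.8 × 20 = 6.4 points. The middle case (0.25 × 0.7 × 15) gives 2.6. Simulating it (100 patients, 4,000 runs) gave 2.5.

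**Does using the earlier scores help?** In simulations with D = 15, p = 0.60 to 0.90 and r = 0.5 or 0.7, a regression estimate using every Group B patient's 6-month score left −0.07 to +0.11 points of bias. When continuing also depended on the unseen later score, one scenario fell from 6.8 to 2.4 points: reduced, not removed.

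**Direction for change scores (70%, OR 2).** The continuers' own 6-month mean is 6.65 points too high and their later mean 3.3 to 4.7 too high. So:
- an all-patient 6-month mean set against the attenders' later mean overstates improvement by 3.3 to 4.7 points;
- change within continuers understates it by 6.65 − 4.65 = 2.0 to 6.65 − 3.3 = 3.3 points.

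**The case against.** The strongest reply is that this is a descriptive case series and the plan is under-specified rather than wrong. Section 12.2 does not exclude a model, and it leaves further tests to a biostatistician. A reader might infer that the plan rules out such an analysis or discards the decliners' data. The documents support neither: decliners' scores enter the Group B summary, and the open clause would permit a model. What remains is that nothing commits to one, and that a descriptive mean still estimates something, which section 3.0 says is the outcome in recipients.

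The reply on size also has force. Participation, selection and correlation are all assumed. With 60 to 90 attenders the standard error of a mean is 35/√60 = 4.5 to 35/√90 = 3.7 points, so the bias is often smaller than sampling error. The 15-point figure was set for a two-group comparison in Group B, and the Extension has no score threshold of its own. It serves here only as a scale.

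Third, a model does not reach everything. The Forgotten Joint Score and the long-leg X-ray have no earlier values. For revised or re-operated patients, a model would supply later means as though the knee had not been revised, which is a different quantity and must be stated. These points stand and limit the fix.

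**Conclusion.** The concern holds as a conditional one. The committed analysis describes attenders, the objective names recipients, and the scores that could link the two have no planned use in the Extension. If continuing depends on the 6-month score, the Knee Society mean at later visits is too high by roughly 0.7 to 1.6 points with 90% continuing, 3.3 to 4.7 with 70%, and 6.2 to 8.7 in the extreme case. All of these rest on SD 35 and the assumed correlation of 0.5 to 0.7. If continuing is unrelated to outcome, there is no bias.

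Two stronger readings go beyond the documents. One is that a bias of over half the 15-point difference should be expected: only the upper end of the extreme case reaches that, and no stated figure points to it. The other is that any later improvement would be partly selection: no 6-month to 5-year contrast is planned, and under the same mechanism change within continuers is understated.

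The repeated-measures model needs a weaker assumption than the attenders' mean does: missing at random given earlier scores, rather than continuing unrelated to outcome. That makes the change worth making.

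**What to change.** In section 12.2:

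1. For the four instruments collected both before and during the Extension (Knee Society, KOOS, SF-12, VAS), add a likelihood-based repeated-measures model on all Group B patients, decliners included, using every visit from pre-op to 5 years. Use visit as a factor, unstructured covariance and REML. Report model means with 95% confidence intervals at 12 months, 2 years and 5 years beside the observed-case summaries.
2. Report the participation rate, and tabulate pre-op to 6-month scores by continued versus not continued. This table alone would show whether the two groups differed on those scores.
3. State that model means for revised or re-operated patients describe outcomes as if unrevised, and report those patients separately.
4. Add a sensitivity analysis for drop-out that depends on unobserved scores.
5. Keep the Forgotten Joint Score and the Extension-only radiographs descriptive, labelled as applying to participants only.

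The cost is SAP wording and a little more analysis of scores already scheduled, with no new visits or patients. The downside is reliance on missing at random given earlier scores, which cannot be verified from the data; item 4 addresses that.
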